12.1.5 Occurrence of adverse events and adverse drug reactions (by time of onset)

The events to be tabulated are shown in [Table 12.1.5-1](#).

The time to onset of adverse events will be classified into the time categories as shown in [Table 12.1.5-2](#), and the number of subjects experiencing events and the incidences of events by primary SOC and PT will be presented for each category for all events, events leading to death, serious events other than death, events leading to interruption, and events leading to discontinuation. The number of subjects experiencing events and the incidence of events

throughout the entire period, regardless of the time of onset, will also be presented. Discontinued subjects will be included in the denominator when calculating incidence for the time categories included in the tabulation periods shown in [Table 12.1.5-1](#), but will be excluded from the denominator for the later time categories.

Table 12.1.5-1 Events to be tabulated

Period	Tabulation time periods	Events to be tabulated
Entire study period	From the start of study treatment to the end of the follow-up period	
 Events occurring between the start of study treatment and the end of the follow-up period Adverse events of special interest occurring between the start of study treatment and the end of the follow-up period
	From the start of study treatment to the end of the extension period	
 Events occurring between the start of study treatment and the end of the extension period Adverse events of special interest occurring between the start of study treatment and the end of the extension period

Table 12.1.5-2 Time category

Time category (unit: weeks)	Time to onset of adverse event (unit: days)
< 6	< 43
< 12	< 85
12 ≤ < 24	85 ≤ < 169
24 ≤ < 36	169 ≤ < 253
36 ≤ < 48	253 ≤ < 337
48 ≤	337 ≤

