### 8.2.3 Extension period

In addition to the use of conditionally permitted concomitant medications (e.g., anti-itch drugs) used at the start of the screening period, the study drug will be injected into the venous line of the dialysis circuit at the end of each dialysis session for 52 weeks (3 times weekly, 156 times in total). Study treatment in the extension period will be started at Week 6. The dose of the study drug will be determined according to [Table 8.2.2-1](#), and the dose of the study drug from Week 6 to immediately before Week 34 will be determined based on the subject's dry weight before dialysis at Week 6. The dose of the study drug after Week 34 will be determined based on the subject's dry weight before dialysis at Week 34. The study drug will not be administered at Week 58.

If any dialysis circuit trouble precludes injection through the dialysis circuit, the study drug will be administered directly intravenously. If an extra fourth dialysis session is required within the week, the study drug will be administered (up to 4 times weekly). If only the extracorporeal ultrafiltration method is used, the study drug will not be administered.

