### 8.2.5 Rationale for the doses and the duration of treatment

In a Japanese phase II clinical study (Study MR13A9-4), intravenous administration of MR13A9 0.25, 0.5, and 1.0 µg/kg or placebo 3 times weekly for 8 weeks resulted in significant improvement of pruritus in 0.5 and 1.0 µg/kg groups compared with the placebo group. In addition, there was a dose-response relationship showing a constant effect of MR13A9 at doses of 0.5 µg/kg and higher. As for safety, MR13A9 at up to 1.0 µg/kg was tolerated, but adverse events occurred frequently in the 1.0 µg/kg group. The phase II study in the United State (Study CLIN2101) and phase III study (Study CLIN3102) also confirmed the superiority of the MR13A9 0.5 µg/kg group to the placebo group. Based on the above, it was considered appropriate to select 0.5 µg/kg of MR13A9 as the recommended clinical dose.

In Study MR13A9-4, the effect of MR13A9 to improve itching was constant after Week 4, and all adverse drug reactions occurred before Week 6. Accordingly, 4-week and 6-week periods in the double-blind period were established to allow the efficacy and safety evaluations of MR13A9, respectively. In addition, a 52-week extension period was established to assess the safety of long-term treatment with MR13A9 with reference to the "Extent of Population Exposure to Assess Clinical Safety for Drugs Intended for Long-Term Treatment of Non-Life-Threatening Conditions" (ELD Notification No. 592 dated May 24, 1995).

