#### **14.6.1 Adverse events and adverse drug reactions**

For the double-blind period, analysis will include events occurring between the start of study treatment in the double-blind period and the end of the double-blind period. For the entire study period, analysis will include events occurring between the start of study treatment in the double-blind period and the end of the follow-up period.

Adverse events of special interest will also be summarized in the same manner.

1) Incidence of adverse events and adverse drug reactions

The number of events, the number of subjects experiencing events, the incidence of events and its two-sided 95% confidence interval will be presented. For the double-blind period, a Fisher's exact test will be used for comparisons between the placebo group and the MR13A9 0.5 µg/kg group, and the between-group difference in incidence and its 95% confidence interval will be presented.

2) Incidences of adverse events and adverse drug reactions (serious events and events leading to discontinuation)

The numbers of events, the numbers of subjects experiencing events, and the incidences of events will be presented for all events, events leading to death, serious events other than death, and events leading to discontinuation.

3) Occurrence of adverse events and adverse drug reactions

The number of subjects experiencing events and the incidence of events will be presented for all events and by primary SOC and PT.

4) Occurrence of adverse events and adverse drug reactions (by severity)

The numbers of events by severity will be presented for all events and by primary SOC and PT.

5) Occurrence of adverse events and adverse drug reactions (by time of onset)

For the entire study period, the number of subjects experiencing events and the incidence of events for all events and by primary SOC and PT will be presented by time of onset.

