 - 6 to 10: 3 points
 - 11 to 13: 4 points

- 14 to 16: 5 points
- Time to onset of an adverse event (days) = Date of onset of the adverse event – Start of study treatment + 1

8. Disposition of Subjects

Analysis for the double-blind period will include subjects who entered the double-blind period. Analysis for the entire study period will include subjects who entered the extension period.

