12.1 Adverse Events and Adverse Drug Reactions

Unless otherwise specified, the following events will be tabulated.

- Double-blind period
 - Events occurring between the start of study treatment and the end of the double-blind period
 - Adverse events of special interest occurring between the start of study treatment and the end of the double-blind period
- Entire study period
 - Events occurring between the start of study treatment and the end of the follow-up period

- Events occurring between the start of study treatment and the end of the extension period
- Adverse events of special interest occurring between the start of study treatment and the end of the follow-up period
- Adverse events of special interest occurring between the start of study treatment and the end of the extension period

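### SAP Table 12.1.5-2 has no 6 to < 12 week row, so adverse events in the placebo-to-MR13A9 group's first six weeks on drug are tabulated only together with placebo time

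*SAP*

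**What the plan says.** - **Clock.** SAP Section 7 defines time to onset as "Date of onset of the adverse event – Start of study treatment + 1". SAP Table 5.7.1-1 puts Day 1 at the start of double-blind treatment. Protocol 14.6.1 does the same for the entire-period tables, which cover "events occurring between the start of study treatment in the double-blind period and the end of the follow-up period". SAP 12.1 adds a second window: "Events occurring between the start of study treatment and the end of the extension period".
- **Switch.** SAP Table 3-2 defines P-MR, in the safety set, as subjects given placebo in the double-blind period who then enter the extension. Protocol 8.2.3: "Study treatment in the extension period will be started at Week 6".
- **Rows.** SAP 12.1.5: "The time to onset of adverse events will be classified into the time categories as shown in" Table 12.1.5-2. In that table the week categories are < 6, < 12, 12 to < 24, 24 to < 36, 36 to < 48, and 48 or more. The day column reads < 43, < 85, 85 to < 169, and so on.
- **Statistic.** SAP 12.1.5: "the number of subjects experiencing events and the incidences of events by primary SOC and PT will be presented for each category". A total "throughout the entire period, regardless of the time of onset, will also be presented".
- **Comparison within the SAP.** Section 10.4 reports average dose for P-MR separately for Weeks 1 to 6 and Weeks 7 to 58, with no overall figure. MR-MR does get an overall figure.

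**The concern.** For P-MR, '< 6' is placebo time and the rows from 12 weeks on are MR13A9 time. '< 12' spans both. No entire-period adverse event table begins at P-MR's first MR13A9 dose, so that group's first six weeks on drug have no row of their own.

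This is the window that the protocol itself picks out. Protocol 8.2.5 justifies the six-week double-blind period by noting that in MR13A9-4, with 8 weeks of dosing, "all adverse drug reactions occurred before Week 6". The plan allows for up to 86 placebo subjects, fewer any who do not enter the extension, to start MR13A9 at Week 6. Their early adverse event incidence is useful supporting information for the safety objective. The same tables are produced at the Week 34 interim tabulations, which SAP 6.3.2 links to the approval application.

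**Working it through.** **1. Reproduce the table's cut-points.** Time to onset is onset date minus start plus 1, so a boundary at w weeks falls at day 7w + 1. For w = 6, 12, 24, 36 and 48 this gives 43, 85, 169, 253 and 337, which matches Table 12.1.5-2. The week and day columns agree for the '< 12' row, so its missing lower bound does not look like a text-extraction fault.

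**2. Place the P-MR switch on this clock.** Week 6 is Day 7 × 6 + 1 = 43. Nominally, Days 1 to 42 are placebo and Days 43 to 84 are the first 42 days on MR13A9.

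**3. Content of the P-MR rows (nominal schedule).**

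| Row | Days | Placebo days | On-drug days |
|---|---|---|---|
| < 6 weeks | 1–42 | 42 | 0 |
| < 12 weeks | 1–84 | 42 (42/84 = 50%) | 42 |
| 12 weeks on, to end of treatment | 85–406 | 0 | 322 |
| Whole period to Week 58 | 1–406 | 42 (42/406 = 10.3%) | 364 |
| Whole period to the Week 34 visit (Day 239) | 1–238 | 42 (42/238 = 17.6%) | 196 |

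**4. Share of on-drug time without its own row.**
- To the end of treatment: 42/364 = 11.5%. The other 322/364 = 88.5% is in rows free of placebo onsets.
- To Week 34: 42/196 = 21.4%. The other 154/196 = 78.6% is in such rows (Days 85 to 238).

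**5. Can the missing row be recovered by subtraction?** Let a be the subjects in '< 6', b the subjects in '< 12', and k those with onsets in both Days 1–42 and Days 43–84. The number with an onset in Days 43–84 is b - a + k. The table does not show k, which can be anything from 0 to a. The true number therefore lies between b - a and b, a range of width a.

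Illustration with assumed incidences (not in the documents), taking the two windows as independent:
- 30% in each window: '< 12' shows 1 - 0.7 × 0.7 = 51%. Subtraction gives 51 - 30 = 21%, so the reader knows only that the figure is between 21% and 51%. The true figure is 30%.
- 10% in each window: '< 12' shows 1 - 0.9 × 0.9 = 19%. Subtraction gives 9%, with a range of 9% to 19%. The true figure is 10%.

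The gap is small for a rare preferred term and large for the all-events line.

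**6. Can the double-blind tables fill the gap?** Not exactly. The double-blind placebo column covers everyone given placebo, whereas P-MR holds only those who entered the extension.

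**The case against.** The strongest reply is that nothing here is wrong. Protocol 14.6.1 asks for presentation by time of onset and sets no categories. The nesting can be read as deliberate: '< 12' is the first of the 12-week bands, and '< 6' is an extra row for the double-blind weeks. Early MR13A9 exposure is already compared with concurrent placebo over six weeks, with 86 subjects planned per group, while the P-MR window is open-label and uncontrolled. Laboratory tests and vital signs are summarised by visit at Weeks 6, 7, 8, 10 and 12 (SAP 12.2.1, 12.3.1). By-subject lists cover deaths, other serious events, interruptions, discontinuations, adverse events of special interest and abnormal laboratory values (SAP 12.6). All of that stands, and it keeps the point minor. None of it supplies a P-MR adverse event incidence for the first six weeks on drug. The table shells are a separate document and were not available.

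A reader might infer that the P-MR whole-period totals are themselves an error, or that placebo time dilutes the reported MR13A9 incidence. The documents do not support that. The totals use the window that the protocol sets, the columns are labelled by sequence group, and no pooled MR13A9 column is specified.

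A fair criticism of a simple repair is that Day 43 is only nominal. The drug is given at the end of dialysis, and SAP Table 5.7.1-1 accepts Week 6 data within 3 days either side. A fixed day boundary could therefore put a few onsets on the wrong side of the switch.

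**Conclusion.** The gap is real, minor and cheap to close. As specified, Table 12.1.5-2 gives no clean incidence of adverse events for P-MR's first six weeks on MR13A9. Those weeks appear only in a row that is nominally half placebo time and in the whole-period total, and row subtraction leaves an uncertainty equal to the '< 6' count.

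The point is limited to the by-onset adverse event tables. P-MR rows from 12 weeks on contain no placebo onsets, and for MR-MR the nested rows mix no treatments. The primary analysis and the randomised double-blind safety comparison do not change. The percentages assume the nominal schedule, and the conclusion assumes that the unseen shells add no further row.

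**What to change.** - Add a disjoint row to Table 12.1.5-2 for 6 to < 12 weeks (43 to < 85 days). If '< 12' is kept, label it as a subtotal.
- For P-MR, assign events around the switch to the placebo row or the MR13A9 row by each subject's actual first MR13A9 dose, not by nominal Day 43. Protocol 10.13.1 collects the date of onset and names no clock time, so the SAP should also state one convention for onsets on the day of that dose.
- Apply both changes to the Week 34 and final tabulations and record them in SAP Section 15.
- Keep the whole-period totals as they are. Separate P-MR tables with onset counted from the first MR13A9 dose are optional. They would also correct for the later P-MR row labels running a nominal 42 days ahead of exposure.

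The cost is one table row and one derived flag. Dosing days (Protocol 10.2) and onset dates are already collected, so no new data are needed. The added row needs no new denominator rule, because every P-MR subject has by definition entered the extension. The only downside is a slightly longer table.

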12.1.6 Details of adverse events of special interest

The events to be tabulated are as follows.

- Double-blind period: Adverse events of special interest occurring between the start of study treatment and the end of the double-blind period
- Entire study period
 - Adverse events of special interest occurring between the start of study treatment and the end of the follow-up period
 - Adverse events of special interest occurring between the start of study treatment and the end of the extension period

The number of events, the number of subjects experiencing events, and incidence of adverse events and adverse drug reactions will be presented. The number of events will be presented by severity (mild, moderate, or severe), action taken with study treatment (drug withdrawn, drug interrupted, dose not changed, unknown, or not applicable), outcome (recovered/resolved, recovering/resolving, not recovered/not resolved, recovered/resolved with sequelae, results in death, or unknown), and time of resolution (during the double-blind period, during the extension period, or after entering the follow-up period).

12.2 Laboratory Tests

Red blood cell count, hemoglobin, hematocrit, white blood cell count, differential white blood cell count (neutrophil, eosinophil, basophil, monocyte, lymphocyte), platelet count, AST, ALT,

γ -GTP, CRP, LDH, ALP, total protein, albumin, glycoalbumin, total cholesterol, total bilirubin, direct bilirubin, creatinine, BUN (before dialysis), Na, K, Cl, Ca, P, serum iron, UIBC, TIBC, TSAT, ferritin, testosterone, free testosterone, prolactin, TSH, FT3, FT4, intact-PTH, and antidiuretic hormone will be analyzed.

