## **10.7 Laboratory Tests**

Blood samples will be collected for the tests listed below before the first dialysis of each week (Monday or Tuesday). Laboratory test values will be determined centrally at the laboratory testing facility. The presence or absence of collected samples will be recorded in the case report form.

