### **10.7.2 Blood biochemistry**

AST, ALT,  $\gamma$ -GTP, CRP, LDH, ALP, total protein, albumin, glycoalbumin, glucose, total cholesterol, total bilirubin, direct bilirubin, creatinine, BUN (before and after dialysis), Na, K, Cl, Ca, P, serum iron, UIBC, TIBC, TSAT, and ferritin

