## 10.10 12-lead ECG

Before dialysis and blood sampling on the first day of each week (Monday or Tuesday), 12-lead ECGs will be obtained in the supine position after a period of rest, and the date of measurement and the assessment by the doctor will be recorded in the case report form. The same testing device will be used in the same subject throughout the study period in principle.

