## 14. Statistical Analysis

Major analysis methods are described below. Details will be specified in a statistical analysis plan prepared separately before the informed consent procedure of the first subject.

For the double-blind period, data from the start of the screening period to the end of the double-blind period will be analyzed. Over the entire study period, data from the start of the screening period to the end of the follow-up period will be analyzed.

Handling of subjects and data in the double-blind period and over the entire study period will be determined before the respective database lock points in the double-blind period and over the entire study period.

All statistical tests will be performed using a two-sided significance level of 5%; however, a two-sided significance level of 15% will be used for the analysis of between-group demographic imbalance. Summary statistics to be presented include the number of subjects, mean, standard deviation, minimum, median, maximum, and quartile.

Data will be tabulated by group and by time point, unless otherwise specified. Baseline is defined as the start date of treatment.

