#### **14.6.3 Laboratory tests**

For quantitative values, summary statistics as well as scatter plots and shift tables before and after treatment will be presented.

For qualitative values, the number and percentage of subjects as well as shift tables before and after treatment will be presented.

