Statistical Analysis Plan

Title of Study: A phase III clinical study of MR13A9 in previously treated hemodialysis patients with pruritus

Protocol No.: MR13A9-5

Version: 3.0

Date of Creation/Amendment: October 24, 2022

Sponsor: Kissei Pharmaceutical Co., Ltd.

Confidentiality Statement

This confidential document contains the sponsor's proprietary information. Any unpublished information contained in the document may not be disclosed without written consent of the sponsor.

Table of Contents

1. Study Objectives.....	3
2. Analysis Sets	3
3. Analysis Groups.....	4
4. General Principles of Statistical Analysis.....	4
5. Handling of Data.....	5
6. Statistical/Analytical Issues.....	6
7. Definition of Derived Data.....	8
8. Disposition of Subjects	10
9. Demographic and Other Baseline Characteristics	10
10. Treatment Compliance.....	12
11. Efficacy	13
12. Safety	18
13. Software Used for Analysis.....	22
14. Tables, Figures and Listing Shells	22
15. Changes from the Clinical Study Protocol	22
16. History of Revision of Statistical Analysis Plan	24
17. Literature References	24

1. Study Objectives

The purpose of this statistical analysis plan is to provide details of the analyses described in “14. Statistical Analysis” of the clinical study protocol (Version, 1.0).

2. Analysis Sets

Analysis sets are defined as follows: When the full analysis set (FAS) and the per protocol set (PPS) are used as analysis sets, analyses will be performed based on the treatment to which each subject has been assigned. When the safety set (SS) is used as an analysis set, analyses will be performed based on the treatment provided to each subject actually.

- 1) FAS
Population of subjects given at least one dose of the study drug, meeting the inclusion criterion related to NRS score, and having a baseline mean NRS score.
- 2) PPS (only in the double-blind period)
Population of subjects excluding the following subjects from the FAS:
 - Subjects not meeting the inclusion criteria
 - Subjects meeting any of the exclusion criteria related to efficacy evaluation
 - Subjects withdrawing from the study before Week 4 in the double-blind period
 - Subjects given < 9 or > 15 doses of the study drug before Week 4 in the double-blind period
 - Subjects changing the dosage and administration of a conditionally permitted concomitant medication or newly using a conditionally permitted concomitant medication before Week 4 in the double-blind period

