- (7) In “11.1.2.4 Change from baseline in the daily NRS score” and “11.2.1.3 Change from baseline in daily itch score,” the text has been updated to include MMRM analysis as performed in the primary analysis.
Reason: To perform an analysis that takes into account the influence of covariates and correlations between time points.
- (8) In “11.2.3 5-D Itch Scale,” component scores (duration, degree, direction, disability, and distribution scores) have been added to the analysis items.
Reason: To perform a more detailed evaluation of the 5-D Itch Scale data.
- (9) In “11.2.2.1 Changes from baseline in Skindex-16” and “11.2.3.1 Changes from baseline in 5-D itch scale,” the variables to be displayed for analysis of covariance have been described.
Reason: To clarify the variables to be displayed.
- (10) In “11.3 Efficacy Subgroups,” the same analysis as described in “11.1.2 Other assessment variables” has been added.
Reason: To perform a more detailed evaluation of the NRS score in subgroups.
- (11) In “11.3 Efficacy Subgroups,” a subgroup defined by the mean NRS score at baseline

(< 6 , ≥ 6) has been added.

Reason: To evaluate whether efficacy varies depending on the mean baseline NRS score.

(12) In “12.1.6 Details of adverse events of special interest,” “adverse events of special interest occurring between the start of study treatment and the end of the extension period” has been added to the events to be tabulated in the entire study period.

Reason: To perform a more detailed evaluation of adverse events of special interest.

(13) In “12.4.1 Evaluation of dependency based on judgment by dependency assessment members,” the description of the target assessments (interim and final) has been added.

Reason: To clarify the target assessments.

3) Changes in the statistical analysis plan version 3.0

(1) “11.2.1.5 Percentage of subjects with improvement in night-time mean itch score” has been added.

Reason: To evaluate in more detail of the improvement in night-time itching.

16. History of Revision of Statistical Analysis Plan

Version	Date of creation/revision	Author	Description
1.0	January 7, 2021	[name]	First version prepared
2.0	November 16, 2021	[name]	Revised version prepared
3.0	October 24, 2022	[name]	Revised version prepared

17. Literature References

- 1) Higaki Y. Skindex-16 (Japanese version): A skin disease-specific quality of life scale. Tokyo. Medical Professional Relations Inc. 2002.

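### SAP 12.2 leaves glucose off the list of laboratory tests to be analysed without recording it, and 12-lead ECG, a declared safety endpoint, has no planned summary in either document

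*SAP*

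**What the plan says.** **Laboratory tests.** The biochemistry panel in protocol 10.7.2 includes the sequence "albumin, glycoalbumin, glucose, total cholesterol, total bilirubin, direct bilirubin, creatinine". Protocol 14.6.3 sets the analysis: "For quantitative values, summary statistics as well as scatter plots and shift tables before and after treatment will be presented". It makes no exception for any analyte.

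SAP 12.2 gives the list of tests that will be analysed. In the same order as the protocol, it reads "total protein, albumin, glycoalbumin, total cholesterol, total bilirubin, direct bilirubin, creatinine, BUN (before dialysis", so glycoalbumin is followed directly by total cholesterol. SAP 12.2.1 to 12.2.3 then specify the summary tables, shift tables and scatterplots.

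SAP 15 records changes from the protocol: none for version 1.0, 13 for version 2.0 and one for version 3.0. Some entries are quite fine. The last for version 2.0, on dependency, says only that "the description of the target assessments (interim and final) has been added". No entry concerns glucose or section 12.2.

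**ECG.** Protocol 4.2.1 lists 12-lead ECG among the safety endpoints. Under protocol 10.10, "the date of measurement and the assessment by the doctor will be recorded in the case report form". Protocol 14.6 has four parts: adverse events and reactions (with events of special interest), vital signs and body weight, laboratory tests, and dependency. SAP 1 states the SAP's scope: "The purpose of this statistical analysis plan is to provide details of the analyses described in" protocol section 14. SAP 12 covers the same four areas plus subgroups and listings. ECG does not appear in the SAP.

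**The concern.** These are two different faults. For glucose, the SAP does less than the protocol promises and does not say so, leaving the reader unable to tell a decision from a slip. For ECG, the SAP follows the protocol faithfully, but the protocol declares an endpoint and then plans nothing for it.

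If the plan is followed as written, there will be no by-group view of glucose values, or of ECG assessments, that were not judged to be adverse events. This covers up to 58 weeks of treatment in hemodialysis patients. The drug-specific reason to look at glucose is limited: protocol 1.3.2.2 names hyperglycaemia among the common adverse drug reactions of one overseas phase II study. What is at stake is the completeness of the descriptive safety report. No between-group test is lost, because no laboratory analyte has one.

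**Working it through.** **Glucose: list against list.** The inputs are protocol 10.7.1 to 10.7.3 and SAP 12.2. The five differential white cell types are counted singly and BUN is counted once.

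| Panel | Protocol | SAP 12.2 | Missing from SAP |
|---|---|---|---|
| Hematology | 10 | 10 | none |
| Biochemistry | 25 | 24 | glucose |
| Endocrinology | 8 | 8 | none |
| Total | 43 | 42 | glucose |

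43 − 42 = 1, and the SAP list contains nothing that the protocol lacks. Post-dialysis BUN is also outside SAP 12.2. It is a second sample of a retained analyte, is taken only at Week −2 (protocol 11.2), and feeds the urea reduction ratio in SAP 7. It is therefore not a second dropped analyte.

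**Planned displays per retained analyte**

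- Summary tables (SAP 12.2.1): 2. The double-blind table has 6 visits + end of period = 7 time points. The entire-study table has 15 visits + end of period = 16.
- Shift tables (12.2.2): 2.
- Scatterplots (12.2.3): 2.
- Total: 2 + 2 + 2 = 6. Glucose receives 0 of the 6.

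**Change log.** 0 + 13 + 1 = 14 entries in SAP 15. None touches the laboratory list.

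**ECG: endpoints against analyses**

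| Safety endpoint (protocol 4.2.1) | Protocol 14.6 | SAP 12 |
|---|---|---|
| Adverse events | 14.6.1 | 12.1 |
| Adverse drug reactions | 14.6.1 | 12.1 |
| Adverse events of special interest | 14.6.1 | 12.1, 12.1.6 |
| Laboratory tests | 14.6.3 | 12.2 |
| Vital signs | 14.6.2 | 12.3 |
| Body weight | 14.6.2 | 12.3 |
| 12-lead ECG | none | none |
| Dependency assessment | 14.6.4 | 12.4 |

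Seven of the eight endpoints have a planned analysis. The by-subject lists in SAP 12.6 do not name ECG either.

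Protocol 11 schedules ECG at Week −2, the start of treatment, and Weeks 6, 12, 34 and 58: six visits, plus discontinuation. Body weight is measured on the same occasions. It has two summary tables (3 + 1 = 4 and 6 + 1 = 7 time points, SAP 12.3.1) and two scatterplots (12.3.2). ECG has no output.

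**The case against.** The strongest reply is that the glucose omission was intended and the rest is already covered.

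- **Intent.** Protocol 14 describes its own scope modestly: "Major analysis methods are described below". Glycoalbumin is kept. Protocol 10.7 says only that "Blood samples will be collected for the tests listed below before the first dialysis of each week", with no fasting requirement, which would make glucose values hard to read. The narrowing of BUN to the pre-dialysis sample shows the list was edited rather than copied. This makes intent plausible, but neither document states it. The BUN restriction is written into the list and has an evident reason; glucose simply disappears.
- **The log is not complete anyway.** SAP 15 also omits additions such as the safety subgroups (12.5) and the tabulation of events leading to interruption (12.1.2). Silence in the log therefore does not prove an error. That is fair, but those are additions. Removing something the protocol plans is the kind of change a reader most needs to see.
- **Weak signal.** The overseas phase II study tested 0.5, 1.0 and 1.5 µg/kg and reported reactions reaching 5% in any active group, so hyperglycaemia cannot be assigned to 0.5 µg/kg. The overseas phase III study (188 subjects on 0.5 µg/kg, 1% threshold) does not list it, and neither do the Japanese phase II studies. For ECG, the overseas single-dose QT study found no clinically significant QTc prolongation, and the nonclinical findings in protocol 1.3.1 are reassuring. All of this stands and keeps the point small.
- **Partial cover.** Findings judged clinically significant become adverse events (protocol 10.13.1.3) and are tabulated by group. Palpitation, tachycardia and syncope are asked about weekly (10.13.5, Appendix 4). ECG charts can be requested when a finding corresponds to an adverse event (19.3). Pulse rate and glycoalbumin are summarised. Abnormal laboratory values are listed by subject (SAP 12.6), although SAP 6.3.1 defers that list past the interim analysis. This is substantial cover. It still gives no group display of values or assessments that fall short of an adverse event.
- **Body weight is an imperfect comparator.** It is numeric, whereas protocol 10.10 states no categories for the ECG assessment. That limits the form an ECG table can take, but not the case for having one.

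**Conclusion.** Both omissions are confirmed on the text, and the point is minor. Glucose is the only one of 43 analytes without a planned analysis, contrary to protocol 14.6.3 and unrecorded in SAP 15. ECG is the only one of eight declared safety endpoints without one, a gap inherited from the protocol and not a SAP departure.

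Confidence is high that the text omits these items. Nothing here shows that the glucose omission was unintended or that a safety signal is hidden. The count of 43 rests on the convention given with the table. SAP 14 says the table shells are provided separately, so the conclusion concerns the wording of the protocol and SAP only; the shells may already contain these outputs, in which case the SAP text should be brought into line with them.

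**What to change.** **Glucose.** Add it to the list in SAP 12.2, so that it enters 12.2.1 to 12.2.3 and the list returns to 43 of 43. This is the better course, because it restores agreement with protocol 14.6.3. If the exclusion was deliberate, log it with its reason in SAP 15; that makes the plan transparent but leaves glucose without a group summary.

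**ECG.** Add to SAP 12 a table of the number and percentage of subjects by recorded ECG assessment, by group, at the time points SAP 12.3.1 uses for body weight. Add a baseline to end-of-period shift table only if the case report form categories allow one. Record the table in SAP 15 as an addition to protocol section 14. All eight safety endpoints would then have a planned summary.

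**Cost.** One word in a list, one or two descriptive tables on data already collected, and one or two lines in SAP 15. No new assessments are needed and the primary analysis is untouched. If the double-blind outputs have already been produced, the new tables can go into the final tabulation, labelled as added later.
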